NCT02637895
Unique Protocol ID 20150534

Evaluation of the Efficacy of Vortioxetine for Posttraumatic Stress Disorder

Miami PIs: [name].

Miami Co-Investigators: [name], [name]

Emory Sub-Investigators: [name]., [name], [name], Ph.D.; [name].

Version 8, January 22, 2019

I. PROJECT ABSTRACT

Posttraumatic stress disorder (PTSD) is a chronic and common anxiety disorder that follows exposure to an overwhelming traumatic event. The majority of patients with PTSD also meet criteria for other psychiatric disorders and many attempt suicide. Despite its impact on society, little is known about the etiology or pathophysiology of this disorder. PTSD is responsive to pharmacological treatments such as selective serotonin reuptake inhibitors (SSRIs), but response rates rarely exceed 60%, and even fewer patients (20-30%) achieve clinical remission. Thus, there is a clear need to develop novel and improved therapeutics for PTSD.

We will assess the efficacy of vortioxetine using a 12-week, double-blind, parallel-group, placebo-controlled trial of adults with PTSD. Although Vortioxetine has not been approved by the Food and Drug Administration for the treatment of PTSD, it has been approved for the treatment of major depressive disorder and its safety profile is well characterized. In addition to measures of symptomatic improvement in PTSD, we will also assess changes in cognitive function and quality of life. Furthermore, we propose to investigate longitudinally whether certain biological surrogate markers (neurophysiology, genotyping, mRNA) are predictive of treatment response.

II. SPECIFIC AIMS

1. Specific Aim 1 (Primary Aim): To determine the efficacy of Vortioxetine compared with placebo in improving PTSD symptoms.

Hypothesis: PTSD patients randomized to acute therapy (12 weeks) with Vortioxetine will show more improvement in PTSD symptoms compared to patients randomized to placebo, as determined by mean changes in the Clinician-Administered PTSD scale (CAPS-5) score over the course of 12 weeks.

2. Specific Aim 2 (Secondary Aim): To determine the efficacy of Vortioxetine in treating PTSD in terms of overall response rate.

Hypothesis: PTSD patients randomized to acute therapy (12 weeks) with Vortioxetine will have a greater rate of treatment response compared to subjects randomized to placebo, as determined by at least 30% improvement from baseline in CAPS-5 total score and a Clinical Global Impression of Improvement (CGI-I) score of 1 or 2.

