3. Specific Aim 3 (Secondary Aim): To determine the efficacy of Vortioxetine in reducing depressive symptoms in PTSD patients.

Hypothesis: PTSD patients randomized to acute therapy with Vortioxetine will show more improvement in depressive symptoms compared to subjects randomized to placebo, as determined by mean changes in the Montgomery-Asberg Depression Rating Scale (MADRS) score over the course of 12 weeks.

4. Exploratory Aim 1: Startle: To assess fear potentiation, conditional discrimination (AX+/BX-), and fear inhibition using acoustic startle methodology in a classical conditioning paradigm in PTSD patients before and after treatment with Vortioxetine.

Hypothesis: PTSD subjects randomized to 12 weeks of Vortioxetine will have improved fear inhibition as measured by the AX+/BX- paradigm compared to baseline, while placebo subjects will not show improvement.

5. Exploratory Aim 2: Cognition, Functional Capacity, and Quality-of-Life: To assess neurocognitive performance (pre- and post-treatment) with tests shown to be sensitive to PTSD (e.g. learning and memory, concentration and attention, and executive functioning). In addition, to explore performance-based measures of everyday living skills, and measure quality-of-life as indexed by subjective reports.

Hypothesis: Statistically significant changes detected for these variables will be correlated across domains.

6. Exploratory Aim 3: Genotyping and Gene Expression: To explore whether response to Vortioxetine is associated with certain candidate gene polymorphisms previously associated with PTSD, and whether treatment with Vortioxetine alters gene expression patterns differentially in treatment responders and non-responders.

Hypothesis: Polymorphisms of specific candidate genes previously identified as relevant to PTSD will be differentially distributed between responders and non-responders to vortioxetine.

III. SIGNIFICANCE/BACKGROUND

Significance of PTSD and Limitations of Current Pharmacotherapies

PTSD is a common chronic anxiety disorder that is often debilitating and follows exposure to an overwhelming traumatic event. PTSD occurs in approximately 8%-14% of the U.S. population (Breslau et al 1998; Davidson et al 1991; Kessler et al 1995). Rates of PTSD among women in the US are higher than in men being approximately twice that of men 12%-18% (Breslau et al 1998; Resnick et al 1993).

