3) Study period II Treatment (Day 0 to 84): Visits 2 through 9. This is the 12-week period of double-blind placebo-controlled acute treatment. At day 0, EKG for safety monitoring will be conducted. The baseline mRNA sample will be collected. All subjects who continue to meet eligibility criteria will be randomized to one of two groups: Vortioxetine or placebo. Randomization will be performed at a 1:1 ratio into two treatment groups, and both vortioxetine and placebo will be distributed to the patient in blister packs. If a participant is taking 10mg of vortioxetine they will be provided with 2 blister packs at each visit. If a participant is taking 20mg, they will be provided with 4 blister packs. Surrogate marker testing for psychophysiology, mRNA, and neuropsychological testing will be repeated at the completion of the double-blind treatment. Due to the amount of study procedures for certain study visits, we will allow study visits to be done over two days.

4) Follow-Up (Day 84 to 98): Visit 10. Patients will return to the clinic two weeks after the last dose of study medication for assessment of psychiatric status, suicidality, follow-up of any abnormal laboratory or EKG results, and to assist with transition of psychiatric care, if indicated.

See the **Schedule of Events** chart at the end of this section for details of the procedures performed during each visit.

B. Justification of Sample Size

Power Analysis:

Samples of n=60 (2 groups) are associated with reduced but adequate power. Between group differences in change scores of $d=.70$ are detectable with .80 power at $p<.05$. Correlations of

.33 between two variables are detectable with power=.80 in the full sample of 60. Within treatment conditions (n=30) correlations of $r=.50$ are detectable with the same level of power.

C. Informed Consent, Regulatory and Ethical Considerations

The study will be conducted in accordance with Good Clinical Practices (GCP), 21CFR Parts 50 and 56 and all applicable regulatory requirements. Approval for conduct of the study will be obtained from the institutional review boards at both sites.

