2a. At the start of the study, participants will undergo specific laboratory tests, as outlined in the Schedule of Events above. Blood tests include: complete blood cell count (CBC) with differential, thyroid functioning (TSH), and free thyroxine, fasting blood sugar, liver function tests (LFTs), including total bilirubin, a hepatitis panel, and a serum pregnancy test in women of child-bearing potential. Participants also undergo a urine toxicology screen, urine pregnancy test and urinalysis testing. Additional blood or urine tests for disallowed medications or drugs of abuse may be performed during the randomization phase at the discretion of the investigator.

3. Pharmacokinetics Testing

3a. As outlined in the schedule of events, participants will undergo confirmatory laboratory testing at visits 5, 7, and 9. Blood will be drawn and tested to confirm the level of Vortioxetine in the participant's system at the time of their study visit.

J. Exploratory Biological and Neuropsychological Assessments

In addition to the treatment outcome goals, we will examine previously identified genetic risk factors for predictors of treatment response. We will also examine SNPs associated with PTSD which meet genome-wide significance within an ongoing cross-sectional n=8000 Genome Wide Association Study.

Hypothesis 1: Based on our extensive prior experience in examining physiological markers of fear responding, we hypothesize that trauma-exposed individuals with PTSD will exhibit a higher likelihood of responding to PTSD treatment if they display differential physiological signatures of PTSD (e.g. increased dark-enhanced startle and decreased extinction of fear), compared to those without these physiological signatures of PTSD.

Hypothesis 2: Based on our previous work in PTSD identifying significant cognitive and functional capacity deficits, we hypothesize that treatment of with vortioxetine will improve cognitive and functional capacity.

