3c. Response keypad. To assess subject awareness and US expectancy during each experimental session subjects will respond on a response keypad (SuperLab, Cedrus Corp.) in coordination with the EMG startle response monitoring system (SR-LAB, San Diego Instruments). During the fear conditioning sessions subjects will press a button marked "+" if they expect a CS to be followed by the US, a button marked "-" if they do not expect a CS to be followed by the US, and a button marked "0" if they are uncertain of what to expect.

3d. Skin Conductance Level. The skin conductance level will be acquired at a sampling rate of 1 kHz using the GSR module of the Biopac system. Two 5 mm Ag/AgCl disposable electrodes filled with isotonic paste will be attached to middle phalanges of the second and fourth finger of the non-dominant hand.

4. Neuropsychological Battery

4a. Rationale and Test Descriptions. Cognitive function will be assessed by Brief Assessment of Cognition in Schizophrenia (BAC-S) test battery with measures in: (1) list learning, (2) digit sequencing task, (3) token motor task, (4) verbal fluency, (5) tower of London test, and (6) symbol coding subtest. All BAC-S measures will be administered at specified time points, and the total composite z-scores will be compared to baseline total composite z-scores.

Updated January 22, 2019

4b. Performance Based-Measures of Functional Capacity

For the assessment of functional capacity, we will use instrumentation previously developed for use in schizophrenia: the UCSD performance-based skills assessment (UPSA; Patterson et al 2001). The UPSA is the most widely used functional capacity measure in serious mental illness, but suffers from a lengthy assessment format (30 minutes), high-level reliance on props, and geographic specificity. The UPSA-B involves role-play tasks similar in complexity to those that a community-dwelling person is likely to encounter. Administration requires an average of 10 minutes. The UPSA-B's two domains result in a summary score ranging from 0 to 100 and we will use the summary score as the dependent variable.

K. Clinical Care

1. Discontinuation from study

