Case report forms are developed from adaptations of NIH and industry-funded clinical trial protocols in PTSD. Study data will be recorded on paper forms and translated to a digital format without specific patient identifying information. Patient identifiers will be maintained in a separate code book that will be kept in a locked cabinet in the Principal Investigator's office at each site. These data will be preserved on site with periodic monitoring by the primary site. At the end of the study, the databases for the different sites will be merged. Data will be entered sequentially and within a timely manner so that any queries for missing information can be resolved.

B. General Statistical Considerations

Possible risk factors/confounders: We expect the randomization procedure to equalize risk factors across treatment groups; however, we will produce summary statistics to explore any unexpected differences in the values of covariates in the treatment groups. While we do not expect differences in covariates in the treatment groups, it is very likely that the response groups will be different on some relevant clinical variables (e.g., comorbid conditions). However, these should affect only the analyses that include treatment response, and not analyses such as group-related change in CAPS. Thus, we will formally assess response group differences in possible covariates of interest and incorporate any covariates identified that are considered both statistically and clinically relevant as additional main effects for the response-based analyses. Specific types of interaction effects, such as effect modifiers specified a priori, will be the subject of exploratory analysis.

Site effects: Our assumption for the analysis plan and power calculations is that the protocols will be implemented sufficiently comparatively to avoid significant site effects in the results. Given that the randomization will be blocked by site, there is no reason to believe that the

subjects will have a different a priori probability of response or will be significantly different from a clinical perspective. However, we will test for site differences in all outcome measures with appropriate univariate comparisons to ensure that this is not a significant confounder. If there is evidence of significant site differences in response, we will proceed with stratified analyses in place of the proposed analyses.

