Appendix B. Description of Scales

Brief Assessment of Cognition in Schizophrenia (BACS)

The Brief Assessment of Cognition in Schizophrenia (BACS) is a clinician-rated instrument that measures cognitive function. The domains of cognitive function that are assessed by the BACS include verbal memory, working memory, motor speed, attention, executive functions and verbal fluency. It is designed to require about 30 min of testing time. BACS A will be performed at V1 and Version B will be performed at V9.

UCSD Performance-Based Skills Assessment- Brief Version (UPSA-B)

The UCSD Performance-Based Skills Assessment (UPSA-Brief) is a role-play test designed to evaluate a person's functional capacity in two selected areas of basic living skills. The UPSA-Brief (UPSA-B) was developed as an abbreviated alternative to the full version of the UPSA ([Mausbach et al., 2007](#)) and contains 2 of the original 5 subscales of the full UPSA (i.e., finance and communications subscales), which allows for shorter administration time (10–15 minutes) and reduced reliance on testing props. An UPSA-Brief Total Score (range = 0–100) is then obtained by summing the subscale scores.

Clinical Global Impressions Improvement Scale (CGI-I) and Severity Scale (CGI-S)

The CGI-I (Guy 1976) is a clinician-rated instrument that measures the degree of the patient's improvement. It is a 7-point scale where 1 = very much improved; 4 = no change; and 7 = very much worse. Baseline for assessing improvement for the CGI-I ratings will be the patient's clinical status at Visit 3. The CGI-S is a similar clinician-rated instrument that measures the overall severity of the patient's illness as compared to the overall study population. It is also a 7-point scale where 1 = normal, not at all ill; 4 = moderately ill; and 7 = among the most extremely ill patients.

Clinician-Administered PTSD Scale (CAPS-5)

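### The startle hypothesis and the BACS comparison are worded against baseline; neither names the drug-versus-placebo difference in change that the randomized design supports

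*Combined protocol and SAP*

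**What the plan says.** **Startle.** The Exploratory Aim 1 hypothesis (Section II) is that the vortioxetine group "will have improved fear inhibition as measured by the AX+/BX- paradigm compared to baseline, while placebo subjects will not show improvement". It names both arms, but as two separate expectations about change from baseline.

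**BACS.** Section V.J.4a says that "the total composite z-scores will be compared to baseline total composite z-scores" and mentions no arm. Appendix B adds that "BACS A will be performed at V1 and Version B will be performed at V9", so every patient changes form between the two assessments.

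**Other cognition text.** Section V.J, Hypothesis 2, expects that "treatment of with vortioxetine will improve cognitive and functional capacity", with no comparator. The Exploratory Aim 2 hypothesis is about correlation: "Statistically significant changes detected for these variables will be correlated across domains".

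**Comparison with the main aims.** Specific Aim 1 is written as drug versus placebo: vortioxetine patients "will show more improvement in PTSD symptoms compared to patients randomized to placebo". Specific Aims 2 and 3 follow the same form.

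**General text.** Section V.B gives power for "Between group differences in change scores of" d = .70 but ties it to no outcome. Section VII.B refers to change in CAPS by group as an example. It sets out repeated-measures mixed models and an intent-to-treat approach for all randomized patients with baseline measures. It does not name a treatment contrast for startle or the BACS.

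**The concern.** Change from baseline in one arm mixes any drug effect with whatever else changes between V1 and V9. For the BACS this can include a difference between the forms, practice and the passage of time. Only the placebo arm separates these from the drug.

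The startle wording has a second weakness. Significant improvement in one arm and none in the other is not a test of the difference between arms, and a non-significant placebo change does not show that placebo patients failed to improve. Taken as a criterion, the wording could support a drug effect that is not there. It could also reject a real one because placebo patients improved too.

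What is at stake is the reading of two exploratory results.

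**Working it through.** **Inputs from the documents.** 30 patients per arm (Section VIII.A), 1:1 allocation (Section V.A), and d = .70 with power .80 at p<.05 (Section V.B).

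**Assumptions.** The documents give no SD, effect size or expected placebo change for either outcome. I therefore assume a shared improvement s, in SD of change, the same in both arms. I also assume normal changes with equal SD, two-sided 0.05, independent arms, and V9 data on all 60 patients.

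**Step 1: the plan's own between-group figure.** For a two-sample t-test on change scores, the noncentrality is 0.70 × √(30/2) = 2.711, with 58 df and critical value 2.002. Power is 0.760 (0.774 by normal approximation; 0.850 by a one-sided t-test), against the stated .80. This is a separate, small discrepancy and nothing below turns on it.

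**Step 2: test against baseline in the vortioxetine arm, no drug effect.** This is a paired t-test with 29 df, critical value 2.045 and noncentrality s√30. Let p(s) be the chance of significant improvement.

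**Step 3: between-arm test, no drug effect.** The shared change cancels, so the chance of a result in the drug's favour is 2.5% at every s.

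**Step 4: startle pattern, only if it were judged by two within-arm tests.** With no drug effect, the chance that the drug arm is significant and the placebo arm is not is p(s) × [1 − p(s)].

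| Shared improvement s | s√30 | p(s): vortioxetine arm vs baseline | Between-arm test, drug's favour | p(s)[1 − p(s)]: drug yes, placebo no |
|---|---|---|---|---|
| 0 | 0 | 2.5% | 2.5% | 2% |
| 0.2 | 1.10 | 18% | 2.5% | 15% |
| 0.36 | 1.97 | 48% | 2.5% | 25% |
| 0.5 | 2.74 | 75% | 2.5% | 19% |

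The product in the last column cannot exceed 0.5 × 0.5 = 25%. It reaches that near s = 0.37 and falls to 1% at s = 0.8, where both arms are nearly always significant.

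**Step 5: the same pattern with a true drug effect of 0.70 SD.** The chance is p(s + 0.70) × [1 − p(s)]: 94% at s = 0, 81% at 0.2, 52% at 0.36 and 25% at 0.5. The unadjusted between-arm test has 76% power at every s. For shared improvement, the worded pattern therefore detects less only above about s = 0.24; below that it detects more.

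**Step 6: missing V9 data.** The 76% assumes complete V9 data. With 24 per arm the noncentrality is 0.70 × √12 = 2.42 and power is about 66%.

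**The case against.** The strongest reply is that the plan already has the right machinery. Section VII.B makes mixed models for repeated measures the overall approach, includes all randomized patients with baseline values, and mentions change in CAPS by group as an example of its analyses. Section V.B is framed between groups. The startle hypothesis names both arms and can be read as an informal prediction that they differ. The BACS sentence sits under a heading about rationale and test descriptions, so it may only define the outcome as change from baseline.

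Much of this stands. A reader might infer that the plan will judge startle by two paired tests, but no section says so; the startle figures above are conditional on that reading. A reader might infer that the BACS will be tested in one arm alone or with the arms pooled, but neither is stated. A reader might also infer that moving from form A to form B is known to raise scores. Appendix B documents the two forms, not a shift; a harder form B would push the other way.

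What does not stand is that the general text settles the matter. It permits a between-arm test without naming one for these outcomes, while their own wording refers to baseline. Specific Aims 1 to 3 show that the authors state the placebo comparison when they intend it.

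**Conclusion.** The point holds as a gap in specification, at low priority. For startle and the BACS the between-arm contrast is allowed but not named, and the outcome-specific wording, read literally, points to within-arm comparisons.

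If the BACS were judged in the vortioxetine arm against baseline, a shared improvement of 0.2 to 0.5 SD would produce an apparent gain 18% to 75% of the time with no drug effect, against 2.5% for the between-arm test. If startle were judged by two within-arm tests, the false pattern would arise at most about 25% of the time. These figures rest on assumed shifts and complete V9 data. They illustrate the literal wording and are not error rates of a prescribed analysis.

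The documents do not support extending the point to the primary, secondary or safety analyses. Both arms are assessed at V1 and V9, so the proper contrast remains available.

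**What to change.** - **Exploratory Aim 1:** reword the hypothesis to *greater improvement in fear inhibition on vortioxetine than on placebo*, and drop the condition that placebo patients not improve.
- **Section V.J.4a:** state that change from baseline in the BACS composite is compared between arms.
- **Section V.J, Hypothesis 2:** add *compared with placebo*. That sentence also covers functional capacity, so the UPSA-B gains the same comparator.
- **Analysis:** for startle and the BACS, estimate the between-arm difference in change at Week 12 within the planned mixed-model, intent-to-treat framework, accounting for the baseline value, with a 95% confidence interval. Report within-arm change descriptively. If power is quoted, say that it assumes complete V9 data.

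Site handling can stay with the existing site plan. The order of the BACS forms need not change, because it is the same in both arms. The Exploratory Aim 2 correlation hypothesis can stay as a separate analysis.

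The cost is one sentence in each of three places and a short analysis statement. No new data, visits or patients are needed.

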Progress in treating PTSD will also require better understanding of the biological characteristics associated with improvement during treatment. As detailed below, this proposal will use state-of-the-art biological and psychological phenotype measurements to identify moderators and mediators of outcomes with vortioxetine treatment. Through this proposal we are seeking to enhance treatment approaches for PTSD by evaluating the novel compound, vortioxetine, and to apply biological signatures to identify treatment prediction and response. The combined expertise across these sites makes for a unique and complementary research approach. We are not aware of any other research team using these state-of-the-art biological approaches along with expertise in prospective treatment prediction to address these seminal questions in PTSD.

IV. DRUG INFORMATION

A. Investigational Drug: Vortioxetine

Vortioxetine is a newly approved antidepressant with a unique pharmacological profile. It is a potent SSRI and, in addition, has a high affinity for the 5HT_{1D}, 5HT₃, and 5HT₇ receptors where it acts as an antagonist. It is also a 5HT_{1A} agonist and 5HT_{1B} partial agonist. Of particular interest to this PTSD study is the finding that vortioxetine exhibits considerable positive effects on attention, memory, and executive function in patients with major depression, as well as improving performance-based measures of disability.

V. RESEARCH DESIGN AND METHODS

A. Overview of Study

The study design is a 2-site, 12-week, randomized, double-blind, placebo-controlled, parallel-arm, flexible dose trial evaluating the efficacy, safety, and tolerability of Vortioxetine for male and female adult outpatients with PTSD. The primary outcome assessment will occur at 12 weeks. A total of 60 patients will be randomized across the 2 study sites. Subjects must have PTSD symptoms for at least 3 months prior to randomization, and have at least moderate PTSD symptom severity as measured by a score ≥ 28 on the CAPS-5 Past-month version at the screening and baseline visits for inclusion in the study. The study population will be comprised of men and women with PTSD resulting from any form of DSM-5-defined trauma. Combat-related PTSD will not be an exclusion, but no cases with pending litigation or disability claims associated with PTSD will be enrolled.

The 4 study phases consist of the following:

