Hypothesis 3: Based on our pilot data that interventions for PTSD can ameliorate genetic predisposition, we hypothesize that trauma-exposed individuals with PTSD will exhibit a higher likelihood of responding to PTSD treatment if they are carriers of risk alleles of the FKBP5, the ADCYAP1R1 gene and other genes (e.g., DAT, BDNF, COMT, CRHR1, 5-HTTLPR, RGS2, GABRA2), compared to non-carriers of risk alleles. We will also examine gene expression and epigenetic risk factors associated with PTSD as predictors of treatment response. These will

include differential mRNA expression and epigenetic (methylation) marks identified pretreatment, previously associated with differential PTSD risk to identify how modulators of gene function relate to treatment response.

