1. DNA

We will draw DNA on all consenting subjects to evaluate whether carriers of identified risk alleles are associated with response or non-response to voritoxetine.

2. mRNA

We will draw 12 mls of blood at baseline and at week 12 to evaluate the expression of HPA-related mRNA expression.

3. Neurophysiology: Startle Testing

3a. Conditioning sessions. The following methods will allow us to assess fear acquisition, and conditional discrimination (learned safety), as well as the subjects' awareness of reinforcement contingencies in the experiment. The aversive stimulus (US) in these studies will be a 250 ms airblast with an intensity of 80 p.s.i. directed to the larynx as described in similar human fear conditioning studies (Grillon & Davis, 1997; Jovanovic et al. 2005). A compressed air tank connected to polyethylene tubing and controlled by a solenoid switch will emit the airblasts. The conditioned stimuli (CS's) used in the AX+/BX- session (A, B, C and X) will be different colored shapes; in the fear acquisition and extinction sessions the CS's will be neutral pictures. The CS's will be presented on a computer monitor. The pictures and colored shapes will be counterbalanced across subjects. The stimuli will be presented using SuperLab 3.0 for Windows (Cedrus, Inc.) and synchronized with the psychophysiological data acquisition using a DIO card (Measurements Computing, Inc). The psychophysiological data will be collected with Biopac MP150 (Biopac Systems, Inc.). Skin conductance will be acquired concurrently with acoustic startle.

3b. Acoustic startle. The acoustic startle response (eyeblink component) will be measured via electromyography (EMG) of the right *orbicularis oculi* muscle. Two 5 mm Ag/AgCl pre-gelled disposable electrodes will be positioned approximately 1 cm under the pupil and 1 cm below the lateral canthus. All resistances will be less than 6 kilo-ohms. EMG activity is acquired at a sampling rate of 1kHz, amplified and digitized. The startle probe (noise burst) will be a 108-dB [A] SPL, 40-ms burst of broadband noise with a near instantaneous rise time.

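### The genetic aim names no genotype-by-arm contrast, so an allele that predicts improvement on any treatment could be reported as a predictor of vortioxetine response.

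*Combined protocol and SAP*

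**What the plan says.** All references are to the combined protocol and SAP.

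- **Section II, Exploratory Aim 3.** The aim is "To explore whether response to Vortioxetine is associated with certain candidate gene polymorphisms previously associated with PTSD". The hypothesis is that variants of such genes "will be differentially distributed between responders and non-responders to vortioxetine".
- **Section V.J.1, DNA.** "We will draw DNA on all consenting subjects to evaluate whether carriers of identified risk alleles are associated with response or non-response" to the study drug. The draw is not restricted by arm.
- **Section V.J, Hypothesis 3.** Trauma-exposed people with PTSD "will exhibit a higher likelihood of responding to PTSD treatment if they are carriers of risk alleles of the FKBP5" gene, ADCYAP1R1 or other genes, with the examples "DAT, BDNF, COMT, CRHR1, 5-HTTLPR, RGS2, GABRA2". The outcome is response to PTSD treatment, not to vortioxetine alone, and no arm contrast is given. The opening of Section V.J adds SNPs from a separate genome-wide study.
- **Section III.** The proposal intends "to identify moderators and mediators of outcomes with vortioxetine treatment", using biological and psychological measures generally.
- **Section VII.B.** Effect modifiers fixed in advance are to be explored, but none is listed. Covariates enter the response-based analyses as main effects. The false discovery rate rule is stated for secondary outcome measures. Section VII has no analysis specific to genetics.
- **Section V.B.** Power is given for a two-group difference, for correlations in all 60 patients, and for correlations within one arm of 30. No figure is given for an interaction.

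**The concern.** A moderator of the drug's effect is a variable across which the drug-placebo difference changes. Comparing responders with non-responders among vortioxetine patients does not estimate that. It estimates the allele's association with improvement on vortioxetine, which mixes any drug-specific effect with natural course, regression to the mean and placebo response. Pooling both arms and comparing carriers with non-carriers has the same limit if genotype enters only as a main effect.

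At stake is the label put on a finding. A marker of general prognosis could enter the literature as a marker of who should receive vortioxetine, while genotyped placebo patients who could show otherwise have no stated role in the analysis.

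**Working it through.** **1. The plan's own within-arm figure.** Section V.B says r = .50 is detectable with .80 power in 30 patients. By Fisher's z, two-sided .05:

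power = Φ(atanh(0.50) × √(30 − 3) − 1.96) = Φ(0.549 × 5.196 − 1.96) = Φ(0.894) = 0.814.

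The figure reproduces. It concerns an association inside one arm and says nothing about a difference between arms.

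**2. How often a purely prognostic allele is significant in the vortioxetine arm.** From the documents: 30 patients per arm (Section VIII.A). Assumed, because the documents give none: 40% carriers, 35% response in non-carriers, the same odds ratio (OR) in both arms (so no drug-specific effect), and a two-sided Fisher's exact test at .05. The documents name no test for this aim.

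Carrier response p₁ = OR × (0.35/0.65) / [1 + OR × (0.35/0.65)]. For OR 3: 3 × 0.538 = 1.615, and 1.615/2.615 = 0.618.

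| Odds ratio | Carrier response | Significant in vortioxetine arm |
|---|---|---|
| 1 (null) | 35% | about 3% |
| 1.5 | 45% | about 5% |
| 2 | 52% | about 10% |
| 3 | 62% | about 21% |
| 4 | 68% | about 32% |
| 5 | 73% | about 42% |

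**3. Other assumed inputs.** With 30% or 50% carriers, and overall response of 60% and 40% or 50% and 50% in the two arms, the Fisher rate is 15–21% at OR 3, 30–43% at OR 5 and 52–74% at OR 10. On the same simulated data, a Wald test of genotype-by-arm is significant in 1–4%. The true interaction is zero here, so about 5% is the most one would want. The lower values partly reflect how conservative that test is in small samples.

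**4. The price of the interaction.** On a continuous change score, with carrier share f and normal approximation, the carrier effect detectable at .80 power within one arm is (1.96 + 0.84)/√(30 f(1 − f)):

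- f = 0.5: 2.80/√7.5 = 1.02 SD
- f = 0.3: 2.80/√6.3 = 1.12 SD

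The interaction is a difference between two such contrasts, so its standard error is √2 times larger. The detectable values become 1.45 SD and 1.58 SD. An interaction of 1.0 SD has power of 49% (f = 0.5) or 43% (f = 0.3).

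**5. Number of genes.** FKBP5, ADCYAP1R1 and the seven listed examples make nine. For nine independent null tests:

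- each at exactly .05: 1 − 0.95⁹ = 37%
- each at the Fisher null rate from step 2 (2.94%): 1 − 0.9706⁹ = 24%

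The gene list is open-ended and the added SNPs are not counted.

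**The case against.** The aim as stated asks about association, and comparing responders with non-responders answers that. The moderator goal is one sentence in the background section and covers many measures. Hypothesis 3 is not confined to vortioxetine, and Section VII.B foresees exploratory effect-modifier analyses that could include genotype. The aim is exploratory, and an interaction in 60 patients would rarely be conclusive. All of this stands, and it rules out several stronger readings that a reader might infer:

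- *That genetic predictors are tested only in the vortioxetine arm, leaving half the genotyped sample unused.* Aim 3 gives a hypothesis, not a test, and Hypothesis 3 is wider. The documents leave the role of placebo patients unstated; they do not exclude them.
- *That the aim cannot answer its own question.* It can answer a question of association. It cannot show that the association is specific to the drug.
- *That a prognostic allele would be reported as a drug predictor.* No reporting rule is given, so the most one can say is that it could be.
- *That the rates in step 2 are false positives.* They are true associations with improvement on vortioxetine. The error would lie in calling them drug-specific.
- *That the gene list carries a 37% false-positive risk.* That needs tests of exact .05 size. Fisher's test at this sample size gives about 24%.

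None of this supplies the missing contrast. The Section VII.B provision depends on modifiers being fixed in advance, and the documents fix none.

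**Conclusion.** The point holds as a gap in specification. No genotype-by-arm contrast is named, so the plan as written gives no way to separate a prognostic allele from one that predicts the drug's effect, although DNA is drawn without restriction by arm.

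The size depends on how strongly the allele predicts improvement. At odds ratios of 1.5 to 2, the vortioxetine-only comparison is significant in 5–10% of trials; at 3 to 5, in 21–42%. These figures rest on assumed carrier share, response rate, odds ratio and test. The structural point does not depend on them.

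The consequence is limited to how exploratory genetic results are interpreted. The primary and secondary efficacy analyses are untouched, so this is a minor but worthwhile improvement.

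**What to change.** In Section VII, add a short analysis paragraph for the genetic aim:

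1. Include genotyped patients from both arms, in a model with genotype, arm and genotype-by-arm.
2. Report the drug-placebo difference in carriers and in non-carriers, and the interaction, each with a 95% interval, as exploratory estimates.
3. Describe a within-arm or pooled result as an association with improvement. Reserve the term predictor of vortioxetine response for findings supported by the arm contrast.
4. Optionally, list the genes in advance and report false-discovery-rate-adjusted p-values across them beside the unadjusted ones.

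This needs wording and some analysis time, and no new samples or visits. The drawback is precision: with 60 patients at most, and fewer if some decline genotyping, the intervals on the interaction will be wide and few alleles will qualify as drug-specific. The plan should say so in advance, so that an inconclusive interaction is not read as evidence that the allele acts alike in both arms.
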